8.3 Data and Safety Monitoring Plan

The PI of the study will have primary responsibility for ensuring that the protocol is conducted as approved by the FHCRC/UW Cancer Consortium Scientific Review Committee and Institutional Review Board. The PI will ensure that the monitoring plan is followed, that all data required for oversight

of monitoring are accurately reported to the FHCRC/UW Cancer Consortium Data and Safety Monitoring Committee (DSMC), that all adverse events are reported according to the protocol guidelines, and that any adverse reactions reflecting patient safety concerns are appropriately reported.

Under the provisions of the FHCRC/UW Cancer Consortium Data and Safety Monitoring Plan (DSMP), Cancer Consortium Clinical Research Support (CRS) provides monitoring for quality process and compliance by qualified monitors unaffiliated with the conduct of the study. Monitoring visits occur at specified intervals determined by the assessed risk level of the study and the findings of the previous visit as described in the Cancer Consortium DSMP.

9.0 STATISTICAL METHODS AND DATA ANALYSIS.

- 9.1 Sample size determination for the second phase of the study.
For all patients treated at a dose of plinabulin of 30 mg/m² or at the MTD the study will follow a Simon 2 two-stage Minimax design.¹⁰ The null hypothesis that the true response rate is 20% will be tested against the one-sided alternative of a response rate of more than 40%. In the first stage, once 18 patients are accrued the study will stop. If there are 4 or fewer responses in these 18 patients, the study will be terminated. Otherwise the study will reopen and 15 additional patients will be accrued. The null hypothesis will be rejected if 11 or more responses are observed in these evaluable 33 patients. This design yields a type I error rate of .05 and a power of 0.8 when the true response rate is 40%. If the true response rate is 20% the probability of ending the trial during the first stage is 0.72. If the true response is 0.4 the probability that the trial will be stopped in the first stage is 0.09. During the initial phase 1 portion of the study 3 or 6 patients will be enrolled for a total sample size of 39 patients.

- 9.2 Efficacy Analysis.
The study population for analyses will include all patients enrolled in the study who receive treatment at the MTD and receive at least one dose of study medication. The primary endpoint will be overall response rate. As noted above, 11 or more observed responses among 33 patients would be considered potentially efficacious and would justify further study. Responses include both complete and partial responses, as defined by RECIST 1.1 criteria. The disease control rate (DCR), defined as the stable disease + partial response rate will be calculated. Toxicity rates will be described as the overall percentage of patients experiencing Grade 3 or higher toxicity.

9.3 Time to event definitions.

Progression free survival is defined as the time from registration until objective tumor progression or death due to any cause, whichever comes first. The date of disease progression will be defined as the earliest date of radiological disease progression as assessed by the investigator using RECIST 1.1 criteria, or clinical disease progression. For patients who have not progressed or died at the time of the analysis, censoring will be performed using the date of the last adequate disease assessment.

Overall survival is defined as the time from registration until the date of death due to any cause. Patients last known to be alive at the time of the analysis will be censored at the date of last contact.

Duration of response is defined as the time between receipt of first study drug and until the date of progression.

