phase 2 open label study of patients with advanced stage lung cancer treated in the second or third line setting with plinabulin and nivolumab.

Endpoints

5.1.1 Primary endpoints.

- For the initial phase. To determine the safety and tolerability of the combination of nivolumab and plinabulin.
- For the subsequent phase, To evaluate the overall response rate, defined as the sum of complete and partial responses according to RECIST 1.1 criteria, of patients treated with a combination of plinabulin and nivolumab.

5.1.2 Secondary endpoints.

- Evaluate disease control rate, defined as the proportion of patients with CR, PR and SD for more than 8 weeks while on combination plinabulin and nivolumab.
- Evaluate duration of response (DOR), Progression Free Survival (PFS) and Overall Survival (OS)
- Determine the safety and tolerability of the combination of nivolumab and plinabulin.

Dose rationale

Plinabulin has been studied as a single agent in a dose escalation study, the maximum tolerated dose was not reached and the recommended phase 2 dose was 30mg/m². A subsequent phase 1 study using plinabulin with docetaxel showed that plinabulin did not contribute to the toxicity of docetaxel⁹. In this study the initial phase will start with a dose of plinabulin of 20 mg/m² and nivolumab at a flat dose of 240mg. If no dose limiting toxicities (DLTs) are seen the dose of plinabulin will be escalated to 30 mg/m²

Treatment plan

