7.4 Plinabulin

Dose delay and/or dose reduction of plinabulin should be considered for significant tumor pain, hypertension, or constipation (including ileus). As a single agent, plinabulin has not been associated with severe hematological toxicity. If a patient experiences a Grade 3 or 4 non-hematologic AE related to plinabulin or the combination of plinabulin with nivolumab, OR requires more than a 14-day delay of scheduled treatment due to toxicity related to plinabulin, regardless of severity, the dose of plinabulin will be reduced per Table 2.

If the same toxicity with same or higher severity recurs despite dose reduction, plinabulin will be discontinued and the patient will continue receiving nivolumab alone. Only one dose reduction for plinabulin is permitted. See [Table 2](#) Dose Modification for Plinabulin.

Treatment with plinabulin will be discontinued permanently for a concomitant elevation of aspartate aminotransferase (AST) or alanine aminotransferase (ALT) levels of more than 3 times the institutional upper limit of normal and bilirubin levels of more than 2 times the institutional upper limit of normal.

Table 2. Dose Modification for Plinabulin.

Condition	Action
First Occurrence of grade 3 or 4 non-hematologic AE assessed as possibly, probably or definitely related to plinabulin	Reduce plinabulin by 10 mg/m ² on subsequent administrations
Second occurrence of Grade 3 or 4 non-hematologic AE assessed as as possibly, probably or definitely related to plinabulin	Discontinue plinabulin (patients may continue on nivolumab alone)
AST and/or ALT > 3 x ULN AND total bilirubin > 2 x ULN assessed as as possibly, probably or definitely related to plinabulin	Discontinue plinabulin (patients may continue on nivolumab alone)

8.0 SAFETY PARAMETERS AND DEFINITIONS:

8.1 Adverse Events:

Adverse events will be collected after the patient has taken the first dose of study drug. After discontinuation from treatment, patients must be followed for all existing AEs for 28 calendar days after the last dose of study drug or until another anti-cancer therapy is initiated.

Clinical Study Protocol 9602
Drug Substance: plinabulin
IND: 129799
Protocol v5.1
Date 7/15/2017

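### Section 9.2 computes disease control rate without complete responses and without the 8-week minimum for stable disease, contradicting the endpoint definition in section 5.1.2

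*Combined protocol and SAP*

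**What the plan says.** DCR is a secondary objective in section 3.0, where it is named but not defined. Two later sections define it.

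- Section 5.1.2, Secondary endpoints: "defined as the proportion of patients with CR, PR and SD for more than 8 weeks while on combination plinabulin and nivolumab".
- Section 9.2, Efficacy Analysis: "The disease control rate (DCR), defined as the stable disease + partial response rate will be calculated".

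The sentence just before the DCR definition in 9.2 concerns the primary endpoint and does include complete responses: "Responses include both complete and partial responses, as defined by RECIST 1.1 criteria".

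The denominator comes from the opening of 9.2: "The study population for analyses will include all patients enrolled in the study who receive treatment at the MTD", with at least one dose of study medication also required.

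Three other places bear on the point. Sections 5.1.4 and 6.6 schedule scans every 8 weeks with a window of one week either way, moving to every 12 weeks after cycle 7. Section 7.4 allows treatment to go on without plinabulin when a toxicity recurs after dose reduction: "plinabulin will be discontinued and the patient will continue receiving nivolumab alone". Section 9.1 gives the patient numbers, 18 at the first stage and 33 evaluable at the end.

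**The concern.** The two definitions can give different values from the same patients, and the protocol does not rank them. Two differences are plain on the page.

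1. **Complete responses.** Section 9.2 leaves them out, so a patient whose disease disappears counts as a success for the response rate and as a failure for disease control.
2. **Duration of stable disease.** Section 9.2 sets no minimum, so SD seen on a single scan counts however soon progression follows.

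At stake is a reported secondary result of a single-arm, open-label trial. With both definitions in current text, the choice between them could be made after the data are seen. If response categories are tabulated under section 9.4, a reader could add the complete responders back. The same table would not show how long each patient's SD lasted, so the second difference could not be undone from it.

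**Working it through.** The protocol states no expected DCR, threshold or test for it, so there is no planned figure to reproduce. The check compares the definitions and then counts patients.

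**Step 1. The definitions side by side.**

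| Element | Section 5.1.2 | Section 9.2 |
|---|---|---|
| CR | counted | not mentioned |
| PR | counted | counted |
| SD | counted if longer than 8 weeks | counted, no minimum |

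**Step 2. The difference as a formula.** Let N be the common denominator, c the number of complete responders, and s the number of SD patients who do not meet the minimum. Assume that the 8 weeks applies to SD only and that all disease control arises on the combination.

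- DCR under 9.2 = (PR + SD) / N
- DCR under 5.1.2 = (c + PR + SD − s) / N
- 9.2 minus 5.1.2 = (s − c) / N

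Each complete responder pulls the 9.2 figure down relative to 5.1.2, and each short SD pushes it up.

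**Step 3. Effect of one patient.** The values of N come from section 9.1 and are used here as assumed denominators.

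- N = 33: 1/33 = 3.0 points
- N = 18: 1/18 = 5.6 points. This applies if the trial ends at stage 1, which the protocol puts at probability 0.72 when the true response rate is 20%.

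**Step 4. Illustration at N = 33.** All counts are assumed: PR = 8, SD = 12, c from 0 to 3, s from 0 to 6. Section 9.2 gives (8 + 12)/33 = 20/33 = 60.6% in every case. Section 5.1.2 gives the following, with 9.2 minus 5.1.2 in brackets, in points:

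| | s = 0 | s = 3 | s = 6 |
|---|---|---|---|
| c = 0 | 60.6% (0.0) | 51.5% (+9.1) | 42.4% (+18.2) |
| c = 1 | 63.6% (−3.0) | 54.5% (+6.1) | 45.5% (+15.2) |
| c = 2 | 66.7% (−6.1) | 57.6% (+3.0) | 48.5% (+12.1) |
| c = 3 | 69.7% (−9.1) | 60.6% (0.0) | 51.5% (+9.1) |

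The 5.1.2 result runs from 14/33 to 23/33 while the 9.2 result does not move. At c = s = 3 the two errors cancel and the figures agree by chance.

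**Step 5. Can short SD arise under this scan schedule?** A nominal 8-week scan with a one-week window falls between 8 − 1 = 7 and 8 + 1 = 9 weeks. If the clock starts at about the first dose, SD seen only at a week 7 or week 8 scan does not establish SD longer than 8 weeks. Section 9.2 would count that patient. Under 5.1.2 it depends on how the duration is measured, and the protocol gives no start date for it. Section 9.3 starts progression-free survival at registration and duration of response at first study drug, and assigns neither to SD.

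**Step 6. Does anything reach the primary analysis?** No. The section 9.1 rule uses CR and PR only. An exact binomial calculation for the stated design (continue past 18 patients with 5 or more responses, reject with 11 or more of 33) gives type I error 0.0458 and power 0.801. The early-stopping probabilities are 0.716 at a 20% response rate and 0.094 at 40%. These agree with the stated .05, 0.8, 0.72 and 0.09, and DCR enters none of them.

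**The case against.** The strongest reply is that little depends on this. DCR has no threshold, test or decision attached. The missing CR looks like a drafting slip, because the neighbouring sentence counts CR as a response. Progression-free survival and dose modifications are planned outputs, so the study team could derive either version from its own data. All of that stands, and it limits the importance of the point. It does not remove the conflict: restoring CR would still leave the SD minimum in one section and not the other, and readers of a published summary will not have the patient-level data.

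A reader might infer a third flat contradiction, because 5.1.2 ends with a reference to being on the combination and 9.2 has none, while section 7.4 lets patients go on with nivolumab alone. The documents do not support stating it that firmly. The phrase may simply name the study regimen, as similar wording does in the primary endpoint of 5.1.1. Its reach over CR, PR and SD is unclear, and 9.2 is silent on disease control first reached on nivolumab alone. It is an ambiguity to clear up.

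A reader might also take N = 39 as a denominator, from "3 or 6 patients will be enrolled for a total sample size of 39 patients". That is strained. Section 9.1 applies the two-stage design to all patients treated at 30 mg/m² or the MTD, which suggests that phase 1 patients at that dose fall within the 33.

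Finally, the 8-week minimum in 5.1.2 could be read as covering CR and PR as well as SD. The two sections would still disagree, so this belongs in the rewording and does not rebut the point.

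**Conclusion.** The contradiction is real on two elements: complete responses and the minimum duration of SD. As written, 9.2 scores a complete responder as lacking disease control and accepts SD of any length. Each patient affected moves DCR by 3.0 points at N = 33 or 5.6 points at N = 18, and the two omissions work in opposite directions, so the 9.2 figure cannot be called conservative or optimistic in advance.

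The per-patient sizes rest on the assumed denominators. The larger gaps in the illustration rest on assumed response counts and show scale only. The formula also assumes that the 8 weeks applies to SD only and that all disease control arises on the combination.

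The on-combination wording is a secondary clarification. The point should be corrected because DCR is a named endpoint, but it does not touch the response-rate decision, the sample size or the error rates.

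**What to change.** Replace the DCR sentence in section 9.2 with one definition and use identical wording in 5.1.2:

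DCR = (CR + PR + SD lasting longer than 8 weeks) / all patients in the section 9.2 analysis population.

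The same wording should settle three details that 5.1.2 leaves open:

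- that the 8-week minimum applies to SD only, if that is the intention;
- the date from which the 8 weeks are counted, given that first scans may fall at weeks 7 to 9;
- whether the on-combination phrase excludes CR, PR or SD first reached on nivolumab alone after plinabulin has been discontinued, or only names the study regimen.

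The last is the authors' choice of endpoint definition and needs no change to treatment rules. The cost is one sentence in each section. No new data are needed, because the scans are already scheduled and section 9.4 already plans to describe study drug administration and dose modifications.

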6.0 STUDY CONDUCT AND TRIAL PROCEDURES

Prior to undergoing any study-specific procedure, patients must read and sign the current Institutional Review Board (IRB)-approved informed consent form. Procedures conducted as part of the subject's routine clinical management (e.g., blood count, imaging study) and obtained prior to signing of informed consent may be utilized for screening or baseline purposes provided these procedures are conducted as specified in the protocol.

Screening

Diagnostic or laboratory studies performed exclusively to determine eligibility for this trial must only be done after obtaining written informed consent. Documentation of the informed consent will be maintained in the patient's chart.

Studies or procedures that were performed per standard of care prior to signing the consent form may be used for baseline values if they fall within the screening specified window (see table 6.10).

The screening visit will occur up to 28 days prior to initiating study treatment. The following should be obtained, [see table 6.10](#).

- Medical History
 - Histologic type of lung cancer diagnosis
 - Prior NSCLC treatment history
 - Medical History
 - Subject demographics
- Physical examination
 - Examination of major organ systems
 - ECOG performance status
 - Height, weight, and vital signs (temperature, blood pressure, heart rate, and respiratory rate),
- Laboratory Evaluations should include:
 - CBC with differential
 - Serum chemistry (sodium, potassium, chloride, carbon dioxide, creatinine, BUN, glucose, calcium, albumin, total bilirubin, AST, ALT, total protein, and alkaline phosphatase)
 - Thyroid function (TSH, T3, Free T4)
 - Pregnancy test (serum or urine) for all women of childbearing potential
- CT scan of known sites of involvement (a prior CT scan that is no more than 28 days before the initiation of treatment may be used).
- Brain MRI or CT (prior MRI or CT scan that is no more than 28 days before the initiation of treatment may be used).

Biopsy

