All subjects who sign consent to participate in this trial will undergo a mandatory biopsy prior to the start of treatment and after 1 cycle of treatment. The biopsy is mandatory but the treating physician must deem the biopsy feasible and safe; if the physician feels that the biopsy is not feasible or it is not safe the subject will still be allowed to enroll in trial. The biopsy will take place at baseline after eligibility criteria has been confirmed and after the first cycle. Tumor tissue samples consisting of core needle biopsies of deep tumor tissue or lymph nodes or excisional, incisional, punch, or forceps biopsies of cutaneous, subcutaneous, or mucosal lesions will be obtained. Fine needle aspirates, cell pellets from effusions or bone biopsies are not permitted. Target lesions considered for core needle biopsies should be deemed suitable for retrieval of at least three cores (minimum diameter 18- gauge). The biopsy will be delivered to the laboratory of [name].

Treatment on Days 1 and 15 of each Cycle.

Cycles are defined as 28 days.

- On Days 1 and 15 of each cycle (+/- 2 days), the following will be performed prior to therapy administration:
 - History and physical examination that includes examination of major organ systems, ECOG performance status (Days 1 only), weight (Days 1 only), vital signs, adverse event evaluation
 - Laboratory evaluations (Days 1 only) including:
 - CBC with differential
 - Serum Chemistry (sodium, potassium, chloride, carbon dioxide, creatinine, BUN, glucose, calcium, albumin, bilirubin, AST, ALT, total protein, and alkaline phosphatase)
 - Thyroid function (TSH, T3, Free T4) will be performed on Day 1 of every ODD cycle

Drug Administration

6.1.1 Dose calculation.

Plinabulin doses will be determined by the patient's actual weight on Day 1 of each cycle, Nivolumab doses are fixed at a flat dose of 240mg.

6.1.2 Schedule of administration.

Patients will receive therapy on days 1 and 15 of a 28 day cycle. Therapy will consist of plinabulin administered via intravenous infusion (IV) over 30 minutes (+/- 5 minutes) followed by nivolumab administered via intravenous infusion (IV) over 60 minutes (+/- 10 minutes).

- Cycles one and two require a 1-hr observation period between plinabulin and nivolumab administration. No observation period will be required in subsequent cycles if infusions were tolerated without any infusion reactions.

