Patients who discontinue treatment without receiving study medication will be replaced. No other patients will be replaced

Clinical Study Protocol 9602
Drug Substance: plinabulin
IND: 129799
Protocol v5.1
Date 7/15/2017

Schedule of events

	Screening ¹	Cycle 1		Cycle 2+		Off Study ¹²	Survival follow up
		Day 1 +/- 2 days	Day 15 +/- 2 days	Day 1 +/- 2 days	Day 15 +/- 2 days		
Informed consent ²	X						
Demographics	X						
Medical history	X						
Concurrent meds	X	X	X	X	X	X	
Physical exam	X	X	X	X	X	X	
Adverse event evaluation		X	X	X	X	X	X ¹³
Vital signs ³	X	X ¹⁴	X ¹⁴	X ¹⁴	X ¹⁴	X	
Height, weight ⁴	X	X		X		X	
Performance status	X	X		X		X	
Biopsy ⁵	X			X			
CBC w/differential	X	X		X		X	
Serum chemistry ⁶	X	X		X		X	
Thyroid Function ⁷	X	X		X ⁷			
Serum pregnancy test	X ⁸						
Disease assessment (CT scan) ⁹	X			8 (±1) weeks, starting in C7 12 (±1) weeks ¹⁰		X	
Brain CT or MRI	X ¹¹	As clinically indicated					
Survival assessment							X
Plinabulin		X	X	X	X		
Nivolumab		X	X	X	X		

1: screening evaluations must be performed within 28 days of Cycle 1 Day 1
2: consent must be performed prior to initiation of any screening or study-specific procedures

Clinical Study Protocol 9602
Drug Substance: plinabulin
IND: 129799
Protocol v5.1
Date 7/15/2017

- 3: vital signs should include: temperature, blood pressure, heart rate, and respiratory rate
- 4: height is needed at screening only
- 5: biopsy is mandatory for all subjects if treating physician deems it to be safe and feasible. If treating physician deems biopsy not safe and/or not feasible the subject may still be enrolled if they meet all other inclusion criteria.
- 6: sodium, potassium, chloride, carbon dioxide, creatinine, BUN, glucose, calcium, albumin, total bilirubin, AST, ALT, total protein, and alkaline phosphatase
- 7: TSH, T3, Free T4 will be performed at screening and Day 1 of every ODD cycle
- 8: serum pregnancy test (for women of childbearing potential only). Subjects must use an acceptable method of birth control.
- 9: CT scan scan of known sites of involvement. A prior CT scan that is no more than 28 days before the initiation of treatment may be used.
- 10: disease will be assessed 8 (\pm 1) weeks, after cycle 7 patients will be reimaged every 12 (\pm 1) weeks.
- 11: brain CT or MRI does not need to be repeated if scans were performed within 28 days of C1D1
- 12: off-study evaluation will be performed within 28 days (\pm 7 days) after last dose of study treatment

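### PFS and OS are timed from registration, but only dosed patients are analysed, so any wait before first dose is counted as survival

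*Combined protocol and SAP*

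**What the plan says.** Section 9.3 (Time to event definitions) gives the same origin to both endpoints. For OS: "Overall survival is defined as the time from registration until the date of death due to any cause". For PFS: "Progression free survival is defined as the time from registration until objective tumor progression or death due to any cause, whichever comes first".

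Section 9.2 (Efficacy Analysis) names a single population for the analyses: "all patients enrolled in the study who receive treatment at the MTD and receive at least one dose of study medication". No separate set is given for PFS or OS.

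Under Replacement of patients in section 6: "Patients who discontinue treatment without receiving study medication will be replaced". No one else is replaced.

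Two entries in section 6 bear on the time before dosing. Screening: "The screening visit will occur up to 28 days prior to initiating study treatment". Biopsy: "The biopsy will take place at baseline after eligibility criteria has been confirmed".

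Registration is not defined anywhere, and no limit is set on the time between it and Cycle 1 Day 1.

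**The concern.** The clock starts at one event (registration), while membership of the analysis set depends on a later one (receiving a dose). A patient who dies between the two is not counted as a death, is not in the denominator, and is replaced by someone who did reach dosing. The patients who remain carry the waiting time as survival. This is immortal time, and it can only lengthen the result.

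At stake are the PFS and OS estimates, both named secondary objectives. The trial has a single arm, so no concurrent group shares the same lag and cancels it. Because registration is undefined, nothing in the plan keeps the lag short or similar between patients.

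**Working it through.** **1. The plan's own figures.** No design figure is stated for PFS or OS. The only stated operating characteristics are those of the two-stage response-rate design in section 9.1 (stop at 4 or fewer of 18; reject the null at 11 or more of 33). An exact binomial calculation gives:

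| Quantity | Stated | Recomputed |
|---|---|---|
| Power at 40% | 0.8 | 0.801 |
| Type I error at 20% | .05 | 0.0458 |
| Early stop at 20% | 0.72 | 0.716 |
| Early stop at 40% | 0.09 | 0.094 |

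The stated power and stopping probabilities reproduce, and the exact type I error is within the .05 limit. None of these figures uses a time origin, so they do not change with this point.

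**2. Can an event fall between registration and first dose in the analysed set?**
- OS: no. A patient who dies before dosing has received no study medication and is outside the section 9.2 set. The guarantee is strict.
- PFS: nearly never. Death is excluded as above, and the schedule of events has no scan between screening and first dose. However, section 9.3 also counts clinical progression, and nothing bars dosing a patient who has progressed clinically beforehand.

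**3. Is a lag foreseen?** The replacement rule has work to do only if patients can enter and then not be dosed. The protocol also uses two reference dates for baseline imaging: inclusion criterion 5 counts 28 days back from enrolment, and the Screening section counts 28 days back from the start of treatment. The length of the lag is not given. I assume 0 to 28 days, taking the top of the range from the screening window.

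**4. Size.** Let g be the lag in months, i.e. days / 30.4375, taken as common to all patients. Each analysed OS time from registration equals the time from first dose plus g, so

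median from registration = median from first dose + g.

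The two nivolumab OS medians in the Background (9.2 and 12.2 months) serve only as a scale:

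| Lag (days) | g (months) | 9.2 becomes | 12.2 becomes |
|---|---|---|---|
| 0 | 0 | 9.20 | 12.20 |
| 7 | 0.23 | 9.43 (+2.5%) | 12.43 (+1.9%) |
| 14 | 0.46 | 9.66 (+5.0%) | 12.66 (+3.8%) |
| 28 | 0.92 | 10.12 (+10.0%) | 13.12 (+7.5%) |

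The documents give no PFS median. For assumed PFS medians of 2 to 4 months, a 14-day lag adds 0.46/4 to 0.46/2, or 11.5% to 23%. A 28-day lag adds 0.92/4 to 0.92/2, or 23% to 46%.

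**5. Deaths removed at the assumed maximum lag.** With a constant hazard from registration, P(death before dosing) = 1 − exp(−ln 2 × g / median). For g = 0.92:
- median 9.2 months: 6.7%, or 33 × 0.067 = 2.2 patients per 33;
- median 12.2 months: 5.1%, or 33 × 0.051 = 1.7 patients per 33.

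Under the same constant hazard, all registered patients timed from registration would have the unshifted median. Either way of aligning origin and population therefore removes the same g.

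**The case against.** The case against is about size and consequence; nothing in the documents resolves the mismatch itself.

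- **The lag is unknown and may be zero.** The 28 days runs from the screening visit to treatment, not from registration to treatment. A reader might infer that every patient gains guaranteed event-free time, perhaps up to four weeks. The documents do not support that: a patient registered on the day of first dose gains nothing. The baseline biopsy does not prove a gap either. It follows confirmation of eligibility, but its place relative to registration is not stated, and patients may enrol without it when it is unsafe or not feasible. This objection stands.
- **No survival comparison is planned.** A reader might infer that the trial's OS will be judged against published nivolumab survival and so look better than it is. The stated hypothesis and the section 9.1 test compare response rate only, and the OS medians are background. Their time origins are not given, so the net bias in an informal comparison cannot be established. This stands.
- **PFS is not strictly protected.** The replacement rule covers patients who were never dosed, not those who worsen and are then dosed. This stands; the strict statement is limited to OS.
- **Duration of response has another origin.** Section 9.3 says: "Duration of response is defined as the time between receipt of first study drug and until the date of progression". Endpoints may differ in origin, and this one is open to question in its own right. It does not show that first dose is right for PFS and OS, and I do not rely on it.
- **The shift is small beside sampling error.** With exponential survival and all 33 deaths observed, an approximate 95% interval around 9.2 months is 9.2 × exp(±1.96/√33), or 6.5 to 12.9 months. That is fair, but a one-directional bias does not average out and here it can be avoided. The plan also names no summary statistic for PFS or OS, so the use of medians is my assumption.

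**Conclusion.** The point holds as a mismatch between time origin and analysis set in two secondary endpoints. Any interval from registration to first dose counts as certain survival for OS and as nearly event-free time for PFS. On an assumed lag of 0 to 28 days the bias is 0 to 0.92 months, and it is never unfavourable. The documents do not show where in that range the trial would fall.

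It does not reach the primary analysis: PFS and OS carry no hypothesis or threshold, and the response-rate rule is unchanged. It is worth correcting before analysis because a stated rule builds in the bias and a change of wording removes it.

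**What to change.** In section 9.3, start PFS and OS at the date of first dose (Cycle 1 Day 1) for the section 9.2 population. The coherent alternative is to keep registration as the origin and analyse all registered patients intended for that dose level, including those never dosed. Under that option registration must be defined and dated relative to Cycle 1 Day 1.

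The first option is a wording change using a date the trial must already record. It does not alter the sample size or the primary analysis. Its cost is that reported PFS and OS times become slightly shorter and deaths before dosing remain outside the dosed set. Reporting how many patients were registered but never dosed, and why, would make that exclusion visible. The alternative retains those deaths, but the PFS and OS population would then differ from the one used for response.
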